This study is designed to evaluate a transdiagnostic CBT specifically constructed to treat Veterans with depressive/anxiety disorders. The protocol includes both a primary transdiagnostic exposure component as well as supplementary disorder-specific modules to address ancillary symptoms. This transdiagnostic CBT has been investigated through focus groups with Veterans and two pilot demonstrations. This study will compare transdiagnostic CBT to an existing evidence-based version of CBT, behavioral activation therapy (BAT; psychotherapy control condition). A randomized controlled trial (RCT) of 96 DVA patients with depressive/anxiety disorders will be conducted to examine its efficacy, feasibility, and accessibility. Diagnostic interviews and self-

report symptom questionnaires will be completed at pre-treatment, immediate post-treatment, and 6-month followup assessment time points.

Research Primary Aim 1: To examine efficacy of transdiagnostic CBT on reducing transdiagnostic and disorderspecific mental health symptoms and improving quality of life at immediate post-treatment and 6-month follow-up. Hypothesis 1: The transdiagnostic CBT will result in significantly greater reductions in symptomatology (for principal and comorbid diagnoses) and improvements in quality of life compared to the BAT control condition at immediate post-treatment and 6-month follow-up. Although limited specific symptoms may ultimately be comparable across treatments (e.g., depression), the transdiagnostic CBT will demonstrate significantly greater reductions in the majority of symptoms (e.g., anxiety, panic, fear, stress).

Research Primary Aim 2: To examine feasibility and acceptability of transdiagnostic CBT

Hypothesis 2: The transdiagnostic CBT will be well tolerated by DVA patients as demonstrated by improved attendance and dropout rates, patient satisfaction questionnaires, and positive feedback in post-treatment patient interviews as compared to the BAT control condition. This hypothesis is based on the predicted greater symptom improvement (hypothesis 1) as well as the flexibility and individual tailoring of the treatment approach incorporated within transdiagnostic CBT.

B. BACKGROUND AND SIGNIFICANCE

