Measures of feasibility and acceptability are dropout proportions (dropout y/n), proportion of sessions attended, proportion of homework assignments completed, and patient satisfaction scores on the STTS-R. 95% CI for proportions will be used to estimate the proportion of participants who exit the study prematurely (drop out) within each intervention group and the difference in dropout proportions between the intervention groups. For the treatment satisfaction and adherence outcomes (STTS-R, proportion of missed sessions or homework assignments), the median and mean responses will be obtained within and between each intervention group. 95% CI for difference in means will be used to estimate the between intervention differences in treatment satisfaction (mean STTS-R) and adherence (e.g. average proportion of missed sessions or homework assignments) for the transdiagnostic CBT versus BAT control conditions. Frequency distributions describing the participants' reasons for noncompliance and discontinuation of participation will be developed.

The GLMM modeling framework described for Primary Aim 1 will be used to compare the effect of transdiagnostic CBT versus BAT control on treatment satisfaction, retention (dropout), and treatment adherence (% missed sessions, % homework completion). Dropout proportions (dichotomous outcome) and % of missed visits and % homework completion will be compared between the intervention groups using GLMM, with logistic/binomial regression analyses as special cases for dichotomous and percentage outcomes; STTS-R will be modeled as a continuous outcome using an appropriate link function. We also will model the longitudinal profile of adherence as a dichotomous outcome at each visit (e.g. attended/did not attend a given session). This will allow us to evaluate the trends in session attendance and to determine if the trends differ by intervention (e.g. whether the probability of missing visits is less/greater at earlier or later time points).

Exploratory Analyses - Diagnostic Groups

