There is a potential psychological risk of emotional discomfort during the assessment and treatment procedures. Although this reaction is not uncommon in exposure-based treatments of anxiety and depression and typically is brief in its duration, there are several provisions to reduce and/or avoid it in the proposed study. First, the proposed treatment will be designed specifically to target the reduction of emotional distress, anxiety, and avoidance. Second, if a participant expresses a desire to discontinue treatment due to distress and/or a study clinician determines that participation is counter-indicated, all research and treatment procedures will be terminated.

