2. ADEQUACY OF PROTECTION AGAINST RISKS

a. Recruitment and Informed Consent

VAMC patients will be recruited from within the Primary Care Mental Health Integration psychotherapy program and CBT Clinic at the RHJ VAMC. All eligible and willing VAMC patients will be required to meet with project staff to review the purpose of the study and review the consent documentation. VAMC patients will be given ample time to discuss the study and ask questions regarding the procedures. Upon thorough review of all documentation, VAMC patients will sign the informed consent document prior to participation in study procedures.

- b. Protection against Risk
- 1. Participants will be made aware of the potential risks and benefits associated with participation and their right to withdraw from the study at any point without any negative impact on their care within the VAMC. Any participants expressing interest in withdrawing from the study will be referred for treatment within the VAMC.
- 2. Participants who appear unable to tolerate the assessment process will be offered a referral to the VAMC and terminated from the study procedures.
- As a member of the mental health service at the VAMC, the Principal Investigator will maintain active collaborations and communications with other VAMC providers to ensure appropriate continuity of care and safeguard against any adverse events.
- 4. All assessors and treatment providers will be trained and supervised by the Principal Investigator, who is a licensed psychologist. At intake, participants identified by clinical interview with both suicidal ideation and acute intent will be excluded from the study and immediately offered emergency psychiatric care at the VAMC. During the duration of the study, the Principal Investigator immediately will contact the participant and assess suicide risk when any instance of suicide risk is identified. If suicidal ideation is present but not intent, the participant will be retained in the study and reassessed for suicide risk by the investigators in one week. In cases of acute suicidal intent, state law requires immediate hospitalization and these guidelines will be followed.

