4. IMPORTANCE OF THE KNOWLEDGE TO BE GAINED

Psychosocial treatments for the depressive/anxiety disorders are greatly limited in the DVA. The limitation may be a result of number of factors, including both VAMC provider and VAMC patient factors. Given the high prevalence of depressive/anxiety disorders in the DVA, the development and evaluation of a new treatment designed to treat VAMC patients with transdiagnostic presentations of depressive/anxiety disorders will represent an opportunity to improvement services and increase access for this population and outweigh the potential risks discussed above.

5. SUBJECT SAFETY AND MINIMIZING RISKS (Data and Safety Monitoring Plan)

The proposed investigation includes a clinical trial that involves the comparison of a newer evidence-based psychotherapy, transdiagnostic CBT, with an established evidence-based psychotherapy, BAT. Both treatment conditions involve active treatments have been shown to be effective in addressing symptoms in the selected disorders/population. Several steps were included in the proposed clinical trial for subject safety and minimizing risks of the research.

- 1. Treatment progress will be assessed throughout the active treatment phase (baseline to final session of psychotherapy) through participant interactions with the project therapist, self-monitoring and other between session exercises, biweekly self-report measures of various psychiatric symptoms (e.g., DASS, IIRS, & STICSA), and immediate post-treatment assessment. Participants who demonstrate worsening of symptoms at any point in treatment (i.e., 25% increase in symptom severity for two consecutive assessment points) or do not demonstrated any symptoms improvement at the midway point in treatment (session 8) will be offered alternative mental health treatments with appropriate VAMC providers. Similarly, alternative mental health treatments with appropriate offered at the 6-month follow-up assessment point to all participants, regardless of symptomatology.
- During the active treatment phase, participants will be monitoring weekly during their psychotherapy appointments. Monitoring will involve interactions with the project therapist, self-monitoring and other between session exercises, and biweekly self-report measures of various psychiatric symptoms (e.g., DASS, IIRS, & STICSA).
- 3. Monitoring will be completed by the project therapist and reviewed by the Principal Investigator during weekly supervision meetings.

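### Hypothesis 2's tolerability claim includes no by-arm count of participants who get worse but stay in treatment

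*Combined protocol and SAP*

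**What the plan says.** Section A states the claim and how it is to be shown: "The transdiagnostic CBT will be well tolerated by DVA patients as demonstrated by improved attendance and dropout rates, patient satisfaction questionnaires", together with favourable post-treatment interview feedback, in comparison with BAT. Section D (Feasibility and Acceptability Analyses) sets out what is analysed: "Measures of feasibility and acceptability are dropout proportions (dropout y/n), proportion of sessions attended, proportion of homework assignments completed", and the STTS-R. It adds one descriptive item: "Frequency distributions describing the participants' reasons for noncompliance and discontinuation of participation will be developed". It does not say that this table is split by arm or that distress or safety is a category.

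Under Aim 1, Section D compares the symptom and quality-of-life scales as mean changes and as scores adjusted for baseline. It does not analyse the proportion of participants who worsen.

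Section E recognises the relevant harms:
- E.1.c says of emotional discomfort that "this reaction is not uncommon in exposure-based treatments of anxiety and depression".
- E.5 item 1 defines worsening as a 25% rise in symptom severity at two consecutive assessments. Its stated use is to trigger an offer of other care. It names neither the scale nor the score from which the rise is measured.
- E.2.b item 4 covers suicide risk: "During the duration of the study, the Principal Investigator immediately will contact the participant" whenever such risk is identified.
- E.2.b item 6 sends adverse events to program officers and IRBs, without a definition, a collection schedule or a table by arm.

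**The concern.** Tolerability of an exposure treatment ordinarily includes whether some patients get worse on it. The Aim 2 measures record whether people stayed, attended, did homework and were satisfied. Someone who meets the protocol's own worsening definition, or has a suicide-risk episode, and still completes treatment is scored as having tolerated it. Aim 1 does not fill this gap, because a mean can improve while a minority deteriorates.

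Some of the planned evidence also leans towards people who did well. Feedback interviews are held only with completers of transdiagnostic CBT, so they allow no comparison with BAT and leave out those least likely to have tolerated treatment. Satisfaction is scheduled only at post-treatment and 6 months, while E.1.c ends all research procedures for a participant who wants to stop treatment because of distress.

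At stake is a favourable tolerability statement, carried into the planned grant application, with no figure beside it on how many participants worsened in each arm.

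**Working it through.** The plan gives no harm rate, power or effect size for this question, so there is no stated figure to reproduce. The check is first a reading of the plan, then three calculations.

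**1. What the planned analysis records**

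| Participant's course | Entry in the planned analysis |
|---|---|
| Stops because of distress, or is withdrawn for safety | Expected to count as dropout, compared by arm. The reason goes into a frequency table not specified by arm |
| Worsens, is offered other care, leaves | Expected to count as dropout, not distinguished from other exits |
| Worsens, stays to the end | Not a dropout; contributes only to a mean |
| Suicide-risk episode, stays | Triggers a contact; no analysis variable |
| Psychiatric hospitalisation or suicide attempt, without dropping out | Reported if it becomes known; no analysis variable |

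The last three rows are the gap.

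**2. Can equal means hide unequal worsening?**

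Inputs from Section C (revised-protocol pilot, 23 completers): IIRS 64.3 before and 37.3 after, a change of 37.3 - 64.3 = -27.0. A 25% rise from 64.3 is 0.25 x 64.3 = 16.1, taken as +16.

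Assumptions, since the documents give no values: 5% of BAT and 20% of CBT participants are 16 points worse at post-treatment; the other BAT participants change by -20 and the other CBT participants by -27.

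- BAT: 0.05 x 16 + 0.95 x (-20) = 0.8 - 19.0 = -18.2
- CBT: 0.20 x 16 + 0.80 x (-27) = 3.2 - 21.6 = -18.4

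The means differ by 0.2 points, while worsening is four times as frequent in one arm (of 48, about 2 against about 10 participants). This shows what is possible; it is not a forecast.

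**3. Precision of a by-arm table**

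Input: 48 per arm (Section D, Randomization Procedures). The 95% half-width for a difference with the same rate p in both arms is 1.96 x sqrt(2p(1-p)/48).

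- p = 5%: 8.7 points
- p = 10%: 1.96 x sqrt(0.18/48) = 12.0 points
- p = 20%: 16.0 points

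For zero events in one arm, the two-sided 95% upper limit is 1 - 0.025^(1/48) = 7.4%. At two-sided 0.05, power for 5% against 10% is 15%, and for 5% against 20% it is 61% (49% with 36 completers per arm). The table can describe, but it cannot test for absence of harm.

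**4. Interval between the last two assessments**

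By the note to the visit table, post-treatment is 1 week after the final session and follow-up is 6 months (about 26 weeks) after it: 26 - 1 = about 25 weeks. By the table itself, week ~18 to week ~33 is about 15 weeks. No contact is scheduled in between on either reading.

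**The case against.** The strongest reply is that Hypothesis 2 says what it means by tolerated: attendance, dropout, satisfaction and feedback, under an aim titled feasibility and acceptability. The plan is therefore not inconsistent with itself, and the trial describes itself as preliminary. That stands. The gap lies in what the claim leaves out.

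Harm is also not wholly invisible. Distress and safety exits should enter dropout, which is compared by arm, and reasons for discontinuation are tabulated. The STTS-R form ends with a participant rating of how far treatment helped, although no analysis of it is specified. These points stand too, and they narrow the gap to participants who worsen, or have a serious event, without leaving.

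A reader might infer two stronger points that the documents do not support.

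- *Events after therapy would surface only by chance.* Adverse events must be reported, the Principal Investigator keeps in contact with other VAMC providers, and the 6-month visit repeats the interview and battery. The accurate statement is that nothing is scheduled between the last two assessments.
- *The monitoring periods conflict.* E.5 item 2 says "During the active treatment phase, participants will be monitoring weekly during their psychotherapy appointments", whereas the suicide-risk response in E.2.b runs for the whole study. The first is scheduled monitoring of treatment and the second is a response triggered by an event. Both can hold.

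**Conclusion.** The gap is real but limited. As written, the trial can report that transdiagnostic CBT was well tolerated without counting, by arm, the participants who met its own worsening definition, had a suicide-risk episode, or were hospitalised or attempted suicide while remaining in the study. Large average worsening would show in Aim 1, and exits would show in dropout; worsening in a minority who stay would show in neither.

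The size cannot be given as an expected bias, because the documents contain no deterioration rates. The IIRS example rests on assumed rates and on pilot completers' scores carrying over to the trial.

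It is tempting to make the tolerability conclusion depend on a harm threshold. The plan offers no basis for a failing value, and with about +/-12 points at 10% per arm, or an upper limit of 7.4% after no events in 48, such a rule could not work as a test. Descriptive reporting is what the sample supports, and it matches the plan's reliance on confidence intervals elsewhere.

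**What to change.** Add to the Aim 2 measures in Section D, for all randomised participants with available data, the by-arm proportion and a 95% CI for the difference for:

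1. a 25% increase at two consecutive assessments, computed separately on the DASS, IIRS and STICSA because E.5 names no scale. State in advance the score from which the increase is measured and whether totals or subscales are used;
2. a suicide-risk episode that triggered the Principal Investigator contact in E.2.b item 4;
3. a psychiatric hospitalisation or suicide attempt from randomisation to the 6-month visit, read from the medical record already used for eligibility.

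Split the discontinuation reasons by arm, with distress or safety as a category. Give the denominator for each row. Report any tolerability statement alongside these figures, without a pass or fail threshold, and describe them as unable to exclude excess harm. These are reporting definitions only and leave the clinical rules in Section E unchanged.

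The cost is analysis-plan wording, one record look-up per participant, and a few small tables with wide intervals. No new instrument is needed.
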